1.3 Clinical Data to Date

Psychotherapy. According to the American Psychological Association's criteria for evaluating the extent to which a particular psychosocial intervention model has evidence of treatment efficacy to warrant its dissemination,^{32,33} interpersonal psychotherapy (IPT-A) has been categorized as a "well-established" intervention for adolescent depression.³ In clinical trials, depressed adolescents treated with IPT-A demonstrated fewer depressive symptoms, better social functioning, and better global functioning at the completion of treatment than adolescents in control conditions.²¹⁻²³

Pharmacotherapy. Fluoxetine has a treatment response rate of approximately 60%^{4,13,34,35}. It is one of two antidepressant medications that has FDA approval for use with children and adolescents.

Combined Treatment. Five recent studies have examined the efficacy of a combination of psychotherapy and medication in comparison to psychotherapy alone and/or medication alone, with response rates ranging from 50-70%.³⁵⁻³⁹ Three studies found that the combined treatment approach was significantly more efficacious in reducing depressive symptoms than medication or psychotherapy alone,³⁵⁻³⁷ whereas the other two did not.^{38,39}

1.4 Dose Rationale and Risk/Benefits

Adolescents who received fluoxetine during the acute phase and were responders (CGI-I = much improved or very much improved) will continue their acute phase dosing regimen and will meet with the psychiatrist on a monthly basis. Adolescents who received fluoxetine during the acute phase and were partial responders (CGI-I = minimally improved) will enter the continuation phase on 40mg fluoxetine, and will have their dose increased to 60mg.⁴⁰ Partial responders will meet with the psychiatrist biweekly for the first 2 months and monthly for the second 2 months. Adolescents who received only IPT-A during acute phase and were partial responders (CGI-I = minimally improved) will begin treatment with fluoxetine during the continuation phase, in addition to continuing their IPT-A treatment. The dosage schedule will be 10mg per day for the first week and 20mg per day for the following 5 weeks. If no treatment response is observed by the 6th week, the dosage can be increased to 40mg per day.⁴¹ Pharmacotherapy sessions will be scheduled weekly for the first 4 weeks and biweekly thereafter. Pharmacotherapy sessions will include assessment of vital signs, adverse effects, safety, and symptomatic response.

The major risks of this study are deterioration with study treatment or the experience of side effects with fluoxetine, if prescribed. The benefits to the subjects are having extensive psychiatric assessments and a possible reduction in depressive symptoms and improvement in social and family functioning with study treatment. The treatments provided in this study are empirically-supported treatments for adolescent depression. Many community clinicians are not trained in evidence-based treatments, and so it is

CONFIDENTIAL

possible that adolescents seeking treatment from a community clinic might be at a greater risk for clinical deterioration and might be less likely to demonstrate a clinical improvement than if they received the treatments provided in this study. What is experimental in this study is the criteria for initiating a change in the treatment plan, the timing of a potential change in the treatment plan, and the type of change to the treatment plan. Currently, there are virtually no empirically-derived guidelines to direct clinicians in deciding whether, when, or how to alter a treatment plan for adolescent depression. Consequently, we expect the relation of the anticipated benefits to the risks to be at least as favorable to the subjects as that presented by available non-study treatment.

2 Study Objectives

Aim 1: Assess the feasibility and acceptability of the personalized continuation treatment strategy.

- Hypothesis 1: Adolescents who responded to the acute phase treatment provided in the K23 study and their parents will consent to participate in continuation treatment.
- Hypothesis 2: Adolescents will be adherent to continuation treatment and will complete the continuation treatment protocol.
- Hypothesis 3: Adolescents and parents will report satisfaction with continuation treatment.
- Hypothesis 4: Treating clinicians will report satisfaction with continuation treatment.

Aim 2: Estimate variances of primary and secondary outcomes with the continuation treatment.

- Hypothesis 5: Adolescents who were responders to acute treatment will show sustained response to continuation treatment.
- Hypothesis 6: Adolescents who were partial responders to acute treatment will show significant improvement in depressive symptoms and social and global functioning.

Aim 3: Conduct exploratory hypothesis-generating analyses to inform further development of the personalized continuation treatment strategy to be tested in a subsequent R01 proposal.

3 Study Design

3.1 General Design

Adolescents will receive 16 weeks of continuation treatment. They will be treated by the same clinicians who provided their acute phase treatment. The personalized continuation treatment plan is illustrated below.

Continuation IPT-A. The goal of IPT-A²⁰ is to decrease depressive symptoms by focusing on current interpersonal difficulties and helping the individual improve his or her relationships and interpersonal interactions. This is accomplished through review of the

[figure not shown]
[figure not shown]
adolescent's significant relationships which leads to the identification of the interpersonal problem areas on which to focus the treatment, development of communication and interpersonal problem solving skills, and role-playing. During the Continuation IPT-A sessions, the therapist will continue to emphasize the interpersonal strategies that were learned and practiced during the acute phase, and address any current interpersonal problems before they result in a recurrence of depressive symptoms. Adolescents who have responded to acute phase treatment (CGI-I = much improved or very much improved) will attend 4 biweekly IPT-A sessions followed by 2 monthly sessions. Adolescents who showed a partial response to acute phase treatment (CGI-I = minimally improved) will attend 8 weekly IPT-A sessions followed by 2 monthly sessions.

Continuation Pharmacotherapy. Adolescents who received fluoxetine during the acute phase and were responders (CGI-I = much improved or very much improved) will continue their acute phase dosing regimen and will meet with the psychiatrist on a monthly basis. Adolescents who received fluoxetine during the acute phase and were partial responders (CGI-I = minimally improved) will enter the continuation phase on 40mg fluoxetine, and will have their dose increased to 60mg.⁴⁰ Partial responders will meet with the psychiatrist biweekly for the first 2 months and monthly for the second 2 months. Adolescents who received only IPT-A during acute phase and were partial responders (CGI-I = minimally improved) will begin treatment with fluoxetine during the continuation phase, in addition to continuing their IPT-A treatment. The dosage schedule will be 10mg per day for the first week and 20mg per day for the following 5 weeks. If no treatment response is observed by the 6th week, the dosage can be increased to 40mg per day.⁴¹ Pharmacotherapy sessions will be scheduled weekly for the first 4 weeks and biweekly thereafter. Pharmacotherapy sessions will include assessment of vital signs, adverse effects, safety, and symptomatic response.

Assessments. Assessments will be administered by independent evaluators who are blind to treatment condition. Adolescents will enter continuation treatment at week 16. Assessments will be conducted at week 24 and 32. The week 32 evaluation is already funded through the K23 study. Assessment measures include the Schedule for Affective Disorders and Schizophrenia for School-aged Children-Present and Lifetime Version (K-SADS-PL),⁴² Children's Depression Rating Scale-Revised (CDRS-R),⁴³ Columbia Suicide Severity Rating Scale (CSSRS),⁴⁴ Global Assessment Scale for Children (C-GAS),⁴⁵ Beck Depression Inventory-II (BDI-II),⁴⁶ Social Adjustment Scale-Self-report (SAS-SR),⁴⁷ Conflict Behavior Questionnaire (CBQ),⁴⁸ and Client Satisfaction Questionnaire (CSQ-8).⁴⁹

CONFIDENTIAL

Treatment Phase	Acute	Continuation	
Assessment	Week 16	Week 24	Week 32

R = Responder (CGI-I = much improved or very much improved), PR = Partial Responder (CGI-I = minimally improved), NR = Nonresponder (CGI-I = no change or worsening)

CONFIDENTIAL

This material is the property of the University of Minnesota. Do not disclose or use except as authorized in writing by the study sponsor

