3.2 Primary Study Endpoints

The primary outcome measure is feasibility/acceptability (treatment satisfaction, session attendance, drop-out rates)

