4.4.2 Data Collection and Follow-up for Withdrawn Subjects

In the event of subject withdrawal from the treatment, we will ask permission to contact the family to continue to complete the study evaluations. Subjects will be determined lost to follow-up if they do not respond to 3 phone calls to their primary number.

5 Study Drug

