7.2 Statistical Methods

All statistical analyses will be conducted on the intent-to-treat sample.

- Hypothesis 1: Among families in the acute phase study who are eligible to participate in continuation treatment, the percentage of adolescents and parents

CONFIDENTIAL

who consent to participate in the continuation treatment, and associated 95% confidence intervals will be calculated.

- Hypothesis 2: The mean/median (depending on the distribution) number and proportion of sessions attended by adolescents, as well as the associated 95% confidence intervals, will be calculated. The proportion of adolescents dropping out of treatment prematurely, and the associated 95% confidence interval, will be calculated.
- Hypothesis 3: An overall mean treatment satisfaction rating, and associated 95% confidence interval, will be calculated based on adolescents' and parents' responses on the CSQ-8.
- Hypothesis 4: An overall mean treatment satisfaction rating and the associated 95% confidence interval will be calculated based on clinicians' response on the clinician satisfaction measure.

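### The CSQ-8 is scheduled only at weeks 24 and 32, so families who leave may have no rating and the primary satisfaction mean is likely, though not certain, to be biased upward

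*Combined protocol and SAP*

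**What the plan says.** Section 3.2 makes satisfaction part of the primary outcome: "The primary outcome measure is feasibility/acceptability (treatment satisfaction, session attendance, drop-out rates". Section 3.1 places the CSQ-8 in the assessment battery, whose list ends "and Client Satisfaction Questionnaire (CSQ-8", and gives the timing: "Assessments will be conducted at week 24 and 32". Adolescents enter continuation treatment at week 16. The list is not split by visit, and neither 3.1 nor section 6 describes a CSQ-8 at treatment sessions or at exit.

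For a subject who withdraws from treatment, 4.4.2 says "we will ask permission to contact the family to continue to complete the study evaluations". It adds: "Subjects will be determined lost to follow-up if they do not respond to 3 phone calls to their primary number".

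Section 7.2 opens with "All statistical analyses will be conducted on the intent-to-treat sample". For Hypothesis 3, an overall mean and 95% confidence interval "will be calculated based on adolescents' and parents' responses on the CSQ-8". Section 7.2 does not say whether week 24, week 32 or both supply that mean, or what happens when a rating is missing. Clinician satisfaction (Hypothesis 4) uses a separate instrument, "will be calculated based on clinicians' response on the clinician satisfaction measure", whose timing is also not stated.

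**The concern.** The first scheduled CSQ-8 comes eight weeks after entry (24 − 16 = 8). A family that leaves in that window has given no rating, and will give one only if it agrees to come back for evaluation and can be reached. Calling the sample intent-to-treat does not create the missing scores.

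The missingness is plausibly informative. Section 4.4.1 lists withdrawn consent, three missed appointments, intolerable side effects and significant worsening as grounds for withdrawal. Each could go with low satisfaction. The first two could also go with refusing further evaluation or not answering calls. If the same families are both less satisfied and less often measured, the mean comes mainly from those who stayed and runs high.

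This matters because the study exists to assess feasibility and acceptability (sections 2 and 7.1) and is meant to inform a later R01 (Aim 3). The Study Summary also promises mean satisfaction for each adaptive treatment strategy. With 30 adolescents divided among strategies, one or two absent ratings could shift a group mean noticeably.

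**Working it through.** The plan gives no figure to reproduce. The sample of 30 was chosen on feasibility grounds, with no SD, expected dropout or retention rate. What follows is an illustration under stated assumptions.

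Inputs:
- N = 30 (section 7.1).
- d, the share who drop out: assumed 10% to 40%.
- r, the share of those leavers who still have a usable CSQ-8: 0, 0.5, 0.8 or 1. The documents do not give it.
- g, the satisfaction gap between stayers and leavers: assumed 0.5 to 1.0 SD.
- One rating per family, so n ratings are treated as independent.

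Step 1, the bias. Take the stayers' mean as zero.
- The mean over all enrolled is −g·d.
- Respondents make up a share 1 − d + d·r of the sample, of whom d·r are leavers, so the observed mean is −g·d·r/(1 − d + d·r).
- The difference is bias = g × [(1 − d)/(1 − d + d·r) − (1 − d)].

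Step 2, the case d = 20% (6 of 30 leave).
- r = 0: (0.8/0.8 − 0.8) = 0.20. Times g, this gives 0.10–0.20 SD.
- r = 0.5: (0.8/0.9 − 0.8) = 0.089. Times g, this gives 0.04–0.09 SD.
- r = 1: (0.8/1.0 − 0.8) = 0. No bias.

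Step 3, the full range, as upward bias in SD units for g = 0.5 to 1.0:

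| Dropout d | r = 0 | r = 0.5 | r = 0.8 | r = 1 |
|---|---|---|---|---|
| 10% | 0.05–0.10 | 0.02–0.05 | 0.01–0.02 | 0 |
| 20% | 0.10–0.20 | 0.04–0.09 | 0.02–0.03 | 0 |
| 30% | 0.15–0.30 | 0.06–0.12 | 0.02–0.04 | 0 |
| 40% | 0.20–0.40 | 0.08–0.15 | 0.03–0.05 | 0 |

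The r = 0.5 column also covers the case in which half the leavers go after week 24 and their week 24 rating is used, if those ratings already show the gap g.

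Step 4, the yardstick. The 95% CI half-width is t(0.975, n − 1)/√n in SD units: 0.37 with 30 ratings, 0.40 with 27 and 0.42 with 24. At 20% dropout these are the cases in which all, half or none of the leavers respond. The interval describes sampling error among those who responded. It does not widen to allow for the bias.

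**The case against.** The strongest answer is that the plan separates leaving treatment from leaving evaluation. Section 4.4.2 sets out to keep withdrawn families in the study evaluations, which include the CSQ-8. The week 32 evaluation is already funded through the linked K23 study (3.1), and adolescent and parent are paid $30 and $10 for week 24 (12.3). Asking permission is no defect, since evaluation cannot be compelled. Families who leave after week 24 may already have a rating. Drop-out and attendance are reported with their own confidence intervals as parts of the same primary outcome, so losses would be visible beside the satisfaction mean.

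Much of this stands, and it rules out three stronger readings that a reader might infer.
- That leavers will be largely absent from the satisfaction data. The documents give no retention rate and state an intention to retain.
- That acceptability is overstated as a fact. This needs both non-response and lower satisfaction among non-respondents, and neither is shown.
- That any bias must favour the strategy. Some families may leave for reasons unrelated to satisfaction with care, such as having to pay for medication themselves (5.7). Full responders are also eligible, and some may stop because they are well.

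Nor does 7.2 say that it will average only the ratings received. It does not say how missing ratings are handled.

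The gap itself remains. Retention under 4.4.2 is an intention that depends on permission and on a family answering calls to one number. A reported drop-out rate shows how many left but does not correct the satisfaction mean, and 7.2 does not commit to stating how many families supplied ratings or whether they completed treatment.

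**Conclusion.** The point holds as a risk to one component of the primary outcome. Families who leave, above all before week 24, may have no CSQ-8, and 7.2 has no rule for missing ratings. Given the withdrawal reasons in 4.4.1, upward bias in the Hypothesis 3 mean is the more likely direction, but it is not certain.

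The size cannot be fixed from the documents. At an assumed 20% dropout and a gap of 0.5–1.0 SD it runs from zero, if all leavers respond, to 0.10–0.20 SD if none do. Both are below the half-width of 0.37–0.42 SD. The 0.20–0.40 SD at 40% dropout with no responders is the extreme of the assumed range, not an expectation. The change is still worth making: ratings not collected at exit may not be recoverable later, and collecting them costs little.

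**What to change.** In 3.1 and 4.4.2, add a stand-alone CSQ-8 for adolescent and parent at the withdrawal contact, completed in person, by phone or by mail. Request it separately from permission for the full battery, so that a family declining further evaluation can still give this one rating. Tie it to the withdrawal contact rather than to the last attended session, because for a family that stops coming that session is known only in retrospect.

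In 7.2:
- Use each family's last available rating: week 32, else week 24, else exit.
- Report the number of respondents out of all enrolled, and satisfaction by treatment-completion status.
- Add one sensitivity analysis with missing ratings set to a low value stated in advance, such as the scale minimum or the lowest observed quartile.

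The burden is small. Adolescents already complete the BDI-II at each therapy session (8.4), so brief questionnaires are routine here. The costs are one short form at exit, ratings taken at different times after entry, and a possibly slightly lower reported mean. Some families will still not be reached, which is why the sensitivity analysis is needed as well as the exit form.

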3.2 Primary Study Endpoints

The primary outcome measure is feasibility/acceptability (treatment satisfaction, session attendance, drop-out rates)

3.3 Secondary Study Endpoints

The secondary outcome measures include depressive symptoms Children's Depression Rating Scale (CDRS), Children's Global Assessment Scale (C-GAS), Social Adjustment Scale (SAS-SR), and response status as defined by Clinical Global Impressions Scale (CGI).⁵⁰ Responders will be defined as having a 1 or 2 (much or very much improved), partial responders will be defined as having a 3 (minimally improved) whereas non-responders will be defined as having a 4-7 on the CGI (minimally improved to very much worse).

3.4 Primary Safety Endpoints

Primary safety endpoints include suicidality (Columbia Suicide Severity Rating Scale), side effects (Side Effects Measure), and vital signs (blood pressure, pulse, weight).

4 Subject Selection and Withdrawal

4.1 Inclusion Criteria

- Male and female adolescents ages 12-18
- Completed acute phase treatment and showed at least a partial response to treatment (CGI-I of minimally improved or better ($CGI-I \leq 3$)).⁵⁰

4.2 Exclusion Criteria

- Completed acute phase treatment and were are non-responder to treatment (CGI-I of no change or worsening ($CGI-I \geq 4$)).

4.3 Subject Recruitment and Screening

We will only enroll adolescents who completed acute phase treatment in our linked study ([name], PI, K23MH090216) and showed at least a partial response to treatment (CGI-I of minimally improved or better ($CGI-I \leq 3$)). Adolescents will enter continuation treatment having either received 12 sessions of IPT-A, 16 sessions of IPT-A, or 12 sessions of IPT-A plus fluoxetine.

4.4 Early Withdrawal of Subjects

4.4.1 When and How to Withdraw Subjects

A subject may be withdrawn from the study prior to expected completion for the following reasons:

- Participant or participant's parent(s) withdraw consent
- Participant fails to adhere to protocol requirements (no show to 3 appointments)

CONFIDENTIAL

This material is the property of the University of Minnesota. Do not disclose or use except as authorized in writing by the study sponsor

- Participant experiences adverse side effects to the fluoxetine that are intolerable to the adolescent or the parent.
- Participant experiences a significant worsening in symptoms: the participant will be evaluated by an independent safety monitor if at any time any of the following occur: 1) a suicide attempt, 2) serious suicidal ideation (with a plan and/or intent) and refusal to contract for safety, 3) psychiatric hospitalization, 4) possible need for psychiatric hospitalization, or 5) significant worsening of depressive or other clinical symptoms (CDRS-R > 76 or CGI improvement score > 5). Adolescents will be removed from the study immediately following review if the independent safety monitor deems that the patient requires treatment outside of study protocols or if the treatment provided in the study is contraindicated.

If a subject exits the study for any reason, the participant will be provided with referrals to receive treatment out of the protocol.

4.4.2 Data Collection and Follow-up for Withdrawn Subjects

In the event of subject withdrawal from the treatment, we will ask permission to contact the family to continue to complete the study evaluations. Subjects will be determined lost to follow-up if they do not respond to 3 phone calls to their primary number.

5 Study Drug

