7.1 Sample Size Determination

Statistical experts warn against over-interpreting pilot data for estimating power and effect sizes for larger clinical trials.⁵¹ Consequently, the proposed research study does not aim to evaluate the efficacy of the adaptive treatment strategies. Rather, the sample size was determined by the study aims which are to demonstrate the feasibility and acceptability of implementing the adaptive treatment strategies. With these aims in mind, an intent-to-treat sample size of 30 was selected. A sample size of 30 will help ensure there are enough depressed adolescents in each adaptive treatment strategy to assess feasibility and acceptability.

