7.3 Subject Population(s) for Analysis

All populations.

CONFIDENTIAL

8 Safety and Adverse Events

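### Evaluation after withdrawal is conditional and thinly pursued, so poor outcomes may be selectively missing from an intent-to-treat analysis that has only two post-entry evaluations

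*Combined protocol and SAP*

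**What the plan says.** **Leaving.** Section 4.4.1 introduces its list of reasons with "A subject may be withdrawn from the study prior to expected completion for the following reasons". The reasons are withdrawn consent, three no-shows, fluoxetine side effects that the adolescent or parent finds intolerable, and significant worsening. Worsening leads first to evaluation by an independent safety monitor. The sentence beginning "Adolescents will be removed from the study immediately following review" applies only if the monitor finds that care outside the protocol is needed or that study treatment is contraindicated. Section 8.4 repeats this monitor process.

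**After leaving.** Section 4.4.2 says: "In the event of subject withdrawal from the treatment, we will ask permission to contact the family to continue to complete the study evaluations". It continues: "Subjects will be determined lost to follow-up if they do not respond to 3 phone calls to their primary number".

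**Evaluations.** Under sections 3.1 and 6, adolescents enter at week 16 and are evaluated at weeks 24 and 32. Section 3.1 adds: "The week 32 evaluation is already funded through the K23 study".

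**Analysis.** Section 7.1 states that "an intent-to-treat sample size of 30 was selected". Section 7.2 states: "All statistical analyses will be conducted on the intent-to-treat sample". Section 7.3 reads only "All populations". None of these sections says how a missing week 24 or week 32 outcome is handled, or which denominator the relapse percentage uses.

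**The concern.** Some permitted reasons for leaving are tied to the outcomes being measured. Worsening is close to relapse and to a poor CDRS-R, and families who leave through no-shows or side effects are plausibly less satisfied. Whether such an adolescent is evaluated again depends on permission asked as treatment ends and on the family answering one telephone number.

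An intent-to-treat analysis needs those evaluations. With 30 adolescents and results meant to shape the next proposal, a few selectively missing poor outcomes could make the strategy look better than it was. Treatment satisfaction is exposed as well as the symptom measures, and it is part of the primary outcome in section 3.2.

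**Working it through.** **1. The plan's own figure.** The sample size of 30 cannot be reproduced. Section 7.1 rests it on feasibility and gives no target precision, power or expected drop-out rate. The arithmetic below takes N = 30 as given.

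**2. The sections side by side.** Section 4.4.1 speaks of leaving the study, while 4.4.2 speaks of leaving treatment and of carrying on with evaluations. The two need reconciling. Section 4.4.2 makes continued evaluation conditional, names one contact route, and does not say when the three calls are made or whether the count restarts at each evaluation.

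**3. Which data go missing.**
- Lost before week 24: no post-entry CDRS-R, C-GAS or K-SADS-PL score, and no CSQ-8 or SAS-SR from a study evaluation. No change score over continuation treatment can be formed.
- Lost between weeks 24 and 32: one post-entry evaluation remains. The mixed-effects models in 7.2 can use it; repeated measures ANOVA in its standard form cannot.
- Attendance and drop-out: still recorded, because leaving is itself the event counted.

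**4. Bounds on relapse.** These are assumptions, not protocol figures: 6 of 30 unevaluated, 6 relapses among the other 24, and all 30 as the denominator. The last is a simplification. Section 7.2 defines relapse as re-emergence, timed from recovery, so adolescents who never recovered may not be at risk.

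Evaluated rate = 6/24 = 25%. If a share q of the six missing relapsed, the full-sample rate is (6 + 6q)/30:

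| q | Full-sample rate |
|---|---|
| 0 | 20% |
| 0.25 | 25% |
| 0.50 | 30% |
| 0.75 | 35% |
| 1 | 40% |

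Each unevaluated adolescent adds 1/30 = 3.3 points to the width of the bounds. This holds only for a percentage with all 30 in the denominator and the outcome unknown for those missing. It does not hold for the consent rate (denominator: eligible families) or for drop-out.

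**5. The same check from an assumed true rate.** Observed rate = (true relapses − relapses among the missing)/(30 − m). Section 1.1 cites relapse of 25-50% after acute treatment; the two ends serve here only as illustrative true rates, giving 7.5 and 15 expected relapses. With 75% of the missing relapsed:

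| Missing m | True rate 25% | True rate 50% |
|---|---|---|
| 3 | (7.5 − 2.25)/27 = 19.4% | (15 − 2.25)/27 = 47.2% |
| 6 | (7.5 − 4.5)/24 = 12.5% | (15 − 4.5)/24 = 43.8% |
| 9 | (7.5 − 6.75)/21 = 3.6% | (15 − 6.75)/21 = 39.3% |

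If the missing relapse at the overall rate, the observed rate equals the true rate for every m.

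**6. Mean scores.** If the missing are worse than the evaluated by D standard deviations, the complete-case mean is too favourable by (m/30) × D. For m = 3 to 9 and D = 0.5 to 1.0, this runs from (3/30) × 0.5 = 0.05 SD to (9/30) × 1.0 = 0.30 SD. The 95% half-width at N = 30 is 2.045/√30 = 0.37 SD.

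**The case against.** A reader might infer that adolescents who worsen or miss visits are automatically removed, and that the intent-to-treat sample therefore loses its worst outcomes. The documents do not support that. Withdrawal is permissive, worsening passes through the safety monitor, and 8.4 contains no removal from the study for no-shows or side effects; for adverse drug reactions it has the medication withdrawn and the patient followed. Nor does the plan simply equate stopping treatment with leaving the study, since 4.4.2 sets out to continue evaluations after treatment ends.

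Further points on the other side:
- The text is silent on renewed attempts at weeks 24 and 32; it does not rule them out.
- The consent form was not available here and may already cover later evaluation.
- Week 32 is funded by the linked study and might continue after withdrawal from this one. If so, only week 24 is exposed.
- BDI-II and CGI ratings are taken at each therapy session (8.4), and mixed-effects models use partial data.
- This is a pilot that disclaims an efficacy evaluation. Sampling error is already large: the exact 95% interval for 6/24 is 9.8-46.7%, wider than the 20-40% bounds.

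Most of this stands, and it limits the point to a risk. It does not remove it. Bias adds to imprecision and is not part of it. Session ratings stop when sessions stop, and 7.2 does not assign them to fill missing evaluations. Mixed-effects models rely on data being missing at random, which is doubtful if unrecorded worsening drives the loss, and an adolescent lost before week 24 gives them no post-entry evaluator score. The intention in 4.4.2 is sound, but the means stated for it are thin.

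**Conclusion.** The point holds as a weakness in retention. Post-withdrawal evaluation is conditional on permission asked at exit and is stated to end after three unanswered calls to one number, while every analysis is promised on the intent-to-treat sample. Poor CDRS-R, C-GAS, relapse and satisfaction outcomes may therefore be selectively missing.

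The size cannot be fixed from the documents, which give no exit or non-response rate. Under the assumed 6 unevaluated of 30, an evaluated relapse rate of 25% is compatible with 20-40%. With 3 to 9 missing and 0.5-1.0 SD worse, means shift by 0.05-0.30 SD. It would go too far to conclude that results will look better than they were: the bias is zero if the missing resemble the rest, and smaller if permission is usually given or week 32 continues under the linked study.

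**What to change.** - Reconcile 4.4.1, 4.4.2 and 8.4 so that stopping study treatment is distinct from withdrawing consent to evaluations. Leave the removal criteria and the safety-monitor process unchanged.
- State in the protocol that agreement to the week 24 and week 32 evaluations after stopping treatment is obtained at entry as the default, unless the entry consent already does so. Keep the right to decline.
- Replace the three-call rule with attempts to both adolescent and parent by all contact routes on file, repeated in the week 24 and week 32 windows, before loss to follow-up is declared.
- Confirm whether the linked study's week 32 evaluation continues after withdrawal from this protocol.

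The cost is protocol and consent wording and some coordinator time. No visits are added. Some families will still decline, so the change reduces the loss without abolishing it.
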